# 9.5.3 Visits 2 & 3 (Days 3 & 5), Visits 5 & 6 (Days 10 & 12), Visits 8 & 9 (Days 17 & 19), and Visits 11 & 12 (Days 24 & 26) [Wednesdays & Fridays]

Subjects will undergo the following assessments during these visits:

- Recording of any changes in concomitant medications (see Section 9.6.3 for details)
- Recording of AEs (see Section 10.3 for details). Any occurrence of dialyzer clotting (assessed at each dialysis session) is to be recorded as an AE (see Section 10.3.2).
- (At Visits 2, 3, 5, and 6): Measurement of body weight within 60 minutes pre-dialysis and within 60 minutes post-dialysis (see Section 9.6.4 for details)
- (At Visits 2, 3, 5, and 6): Measurement of vital signs (blood pressure, heart rate, respiratory rate, and oral body temperature within 30 minutes pre-dialysis and within 30 minutes post-dialysis (see Section 9.6.5 for details)
- (Visits 2, 3, 5, and 6 only:) Study drug administration pre-dialysis (immediately after needle placement) (see Section 9.3.5 for details)
- Collection of blood samples for PK assessments pre-dialysis/pre-dose (at the time of needle placement) (Visits 2, 3, 5, 6, and 8), and at the end of dialysis (before needle removal) (Visits 2, 3, 5, and 6) (see Section 9.6.8.3 for details).

# 9.5.4 End-of-Study/Early Termination Visit (Day 29)

Subjects will undergo the following assessments during these visits:

- Recording of any changes in concomitant medications (see Section 9.6.3 for details)
- Recording of AEs (see Section 10.3 for details)
- Complete physical examination (see Section 9.6.4 for details)
- Standard 12-lead ECG within 60 minutes pre-dialysis (see Section 9.6.6 for details)
- Measurement of body weight within 60 minutes pre-dialysis and within 60 minutes postdialysis (see Section 9.6.4 for details)
- Measurement of vital signs (blood pressure, heart rate, respiratory rate, and oral body temperature within 30 minutes pre-dialysis and within 30 minutes post-dialysis (see Section 9.6.5 for details)
- Collection of blood samples pre-dialysis for safety laboratory tests (hematology, CMP, coagulation panel) (see Section 9.6.8.1 for details).

#### 9.6 STUDY ASSESSMENTS

#### 9.6.1 Informed Consent Forms and Subject Log

Written informed consent for participation in the study must be obtained from all prospective subjects before performing any study-specific screening test or procedure. The investigator will maintain a log of all subjects who consented to participating in the study.

# 9.6.2 Medical History and Demographic Data Collection

Details of the underlying condition (including ESRD and dialysis history), as well as general medical history (including clinically significant diseases or conditions, surgeries, and reproductive status), will be recorded at screening/baseline. Baseline complaints (symptoms or adverse experiences present prior to the first dose of study drug) will also be recorded as medical history.

Demographic data will include age, sex, and self-reported race/ethnicity.

# 9.6.3 Baseline and Concomitant Medications

All medications (including over-the-counter medications) or therapy administered to the subject during the 30 days prior to the first dose of study drug will be recorded at screening/baseline (including start date, medication name, dosage, frequency, and route of administration). Any contraindicated medications will be stopped or replaced by different medication and the subject will be required to observe the protocol-specified wash-out period (refer to Section 9.4.1 for details).

Any changes to concomitant medications will be documented regularly throughout the study.

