# 9.4.1 **Prohibited Therapy**

Patients receiving long-term warfarin (Coumadin) frequently develop asymptomatic excessive prolongation of their international normalized ratio (INR) results. The anticoagulant effect of warfarin, functioning by its interference with the clotting effect of vitamin K, can be offset with as little as 1 mg of vitamin K (Crowther et al. 1998). Therefore, use of vitamin K is contraindicated in individuals on warfarin therapy (Vitamin K2 Monograph, 2009).

Medications that are prohibited while the subject is receiving study drug are listed in Table 3.

Table 3 Washout Periods for Prohibited Medications

Prohibited Medication	Minimum Washout Period Prior to the First Dose of Study Drug
Any investigational therapy	4 weeks
Warfarin*	2 weeks
IV antibiotics	2 weeks
Prescription and non-prescription medications known to be sensitive substrates of CYP3A** or CYP4F2***	None
Herbal and homeopathic remedies	None

Abbreviations: IV=intravenous

The investigator should contact the Medical Monitor if questions arise regarding medications not listed above.

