#### 9.5 STUDY VISITS

The schedule of assessments to be performed during the study is provided in **Table 1**. All activities must be performed and documented for each subject.

\* Subcutaneous heparin, enoxaparin and novel oral anticoagulants (NOAC; such as apixaban) are permitted.

\*\* As listed in the FDA *Drug Development and Drug Interactions: Table of Substrates, Inhibitors and Inducers* (2017)

\*\*\* Example: fingolimod

The expected duration of study participation for an individual subject is approximately five weeks, including up to one week for screening, two weeks of study treatment, and two weeks of post-treatment safety follow-up.

Subjects will undergo a total of 14 visits during their study participation: Screening visit (within seven days prior to the first dose of study drug), three visits per week during the two-week treatment, and two-week safety follow-up periods (coinciding with the subject's hemodialysis schedule), and the EOS/Early Termination visit. Baseline assessments will be completed prior to the first study drug intake on Day 1. The EOS/Early Termination visit will occur two weeks after the last dose of study drug (on study Day 29).

Subjects will be closely monitored for safety and tolerability throughout the study. At each treatment visit, assessments should be completed prior to the study drug administration, unless otherwise stated.

At each study visit, subjects will also undergo hemodialysis, as per their standard ESRD management; hemodialysis is therefore not listed as a study-related assessment in the following sections.

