# 9.5.1 Screening Visit (Day -7 to Day -1)

Subjects will undergo the following assessments during screening:

- Obtaining informed consent and Health Insurance Portability and Accountability Act (HIPAA) authorization (see Section 9.6.1 for details)
- Review of eligibility (inclusion and exclusion) criteria (see Sections 9.1.1 and 9.1.2 for details)
- Recording of general medical history (including menstrual history for females of childbearing potential), disease history, and demographics (see Section 9.6.2 for details)
- Recording of baseline and concomitant medications (see Section 9.6.3 for details)
- Complete physical examination, measurement of height and weight (see Section 9.6.4 for details)
- Standard 12-lead ECG within 60 minutes pre-dialysis (see Section 9.6.6 for details)
- Measurement of vital signs (blood pressure, heart rate, respiratory rate, and oral body temperature (pre-dialysis) (see Section 9.6.5 for details)
- Testing for HIV, hepatitis B and C (see Section 9.6.8.1 for details)
- Collection of blood samples for safety laboratory tests pre-dialysis (hematology, CMP, coagulation panel, and serum β-hCG pregnancy test (females of childbearing potential only) (see Section 9.6.8.1 for details).

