# 9.6.8.1 Safety Laboratory Assessments

Samples for the following safety laboratory tests will be sent to the central laboratory for analysis:

- Hematology panel: red blood cell (RBC) count, hemoglobin, hematocrit, and white blood cell (WBC) count, with differential (neutrophils, eosinophils, lymphocytes, monocytes, basophils, and other cells), if clinically indicated.
- Complete Metabolic Panel (CMP):
  - o Glucose, albumin, total protein;
  - Electrolytes: sodium, potassium, bicarbonate, chloride, calcium, magnesium, phosphate;
  - o Renal function tests: blood urea nitrogen (BUN), creatinine;
  - Liver function tests: (ALT, AST, bilirubin), and
  - Lipid profile: total cholesterol, low-density lipoprotein (LDL) cholesterol, high-density lipoprotein (HDL) cholesterol, and triglycerides (TG).
- Coagulation panel includes: partial thromboplastin time (PTT), INR, and platelet count.

All blood sampling will occur pre-dialysis (at the time of needle placement).

In addition, all subjects will undergo the following tests at screening only:

- Serology for:
  - HIV
  - HBV: hepatitis B "e" antigen (HBeAg) and PCR for the active virus (HBV deoxyribonucleic acid [DNA]); and
  - o HCV: HCV antibody and PCR for active virus (HCV ribonucleic acid [RNA])
- For women of child bearing potential only: serum beta-human chorionic gonadotropin (β-hCG) pregnancy test (the results of the screening pregnancy test must be negative for enrolment).

The schedule for laboratory assessments is provided in **Table 1**. All baseline laboratory assessments may occur during screening (within 7 days prior to the first dose of the study drug).

The total volume of blood drawn from each subject for safety laboratory assessment will be approximately 57 mL over the course of the study. Instructions for safety laboratory specimen collection, handling, and shipping will be included in the laboratory manual provided by the Central Laboratory (Covance).

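### Section 9.6.3 directs a stop-and-washout that, for warfarin, IV antibiotics or investigational therapy still in use at screening, cannot finish inside the 7-day screening window (minor subject-safety and consistency point)

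*Combined protocol and SAP*

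**What the plan says.** Section 9.6.3 has the site record all medication from the 30 days before the first dose, and then directs: "Any contraindicated medications will be stopped or replaced by different medication and the subject will be required to observe the protocol-specified wash-out period". It refers to Section 9.4.1 for the periods.

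Table 3 in Section 9.4.1 gives them under the column heading "Minimum Washout Period Prior to the First Dose of Study Drug": 4 weeks for any investigational therapy, 2 weeks for warfarin, 2 weeks for IV antibiotics, and None for two further classes, namely sensitive CYP3A or CYP4F2 substrates and "Herbal and homeopathic remedies". The text above the table describes vitamin K as contraindicated with warfarin, so warfarin is the clearest case to which Section 9.6.3 applies. The Table 3 footnote and exclusion 12 add: "Subcutaneous heparin, enoxaparin and novel oral anticoagulants (NOAC; such as apixaban) are permitted".

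Section 9.5 defines the "Screening visit (within seven days prior to the first dose of study drug", and the heading of Section 9.5.1 reads "Screening Visit (Day -7 to Day -1". Consent is taken at that visit. The same visit includes "Review of eligibility (inclusion and exclusion) criteria (see Sections 9.1.1 and 9.1.2 for details", and the eligibility review is repeated on Day 1 (Section 9.5.2). Section 13.2 requires consent before the protocol may change a subject's ongoing care.

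Exclusions 11 to 13 (Section 9.1.2) look back from the first dose: 2 weeks for severe infection needing IV antibiotics, 2 weeks for warfarin and 4 weeks for an investigational drug. Section 9.3.4 restricts dispensing to subjects who meet all criteria, and Section 14.3 rules out eligibility waivers. No longer screening window, pre-screening washout phase or re-screening is described.

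**The concern.** The instruction in Section 9.6.3 and the visit schedule do not fit together. The only Table 3 classes with a washout to observe are the three whose washout is longer than the screening window. If the drug is still in use at screening, the site is told to stop or replace it and wait, but the schedule leaves too little time to wait.

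The stake is mainly warfarin. Exclusion 12 is anchored to the first dose, so a site could read it as a condition to be met by Day 1 and read Section 9.6.3 as the way to meet it. The site might then stop a consented subject's warfarin, or move the subject to a permitted anticoagulant, before finding that the subject cannot be dosed in that window. That would be an unnecessary or premature change of treatment. For IV antibiotics and investigational therapy, the point is only that the timetable does not work.

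**Working it through.** **Inputs**

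- Days from consent to first dose, s: 7 (consent on Day -7) down to 1 (consent on Day -1). Sections 9.5 and 9.5.1; the schedule has no Day 0.
- Washout, W: 14 days for warfarin and for IV antibiotics, 28 days for investigational therapy. Table 3.
- Days from last intake to consent, d: 0 if the drug is still in use at screening.
- A stop made for the study cannot precede consent. Section 13.2.

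**The plan's own figure.** With no Day 0, Day -7 to Day 29 spans 7 + 28 = 35 days, or 35/7 = 5 weeks. This agrees with the approximately five weeks of participation in Section 9.5 and confirms the day count.

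**Shortfall on Day 1** = max(0, W - s - d). For a drug still in use (d = 0):

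| Class | W | Consent on Day -7 | Consent on Day -1 |
|---|---|---|---|
| Warfarin | 14 | 14 - 7 = 7 days | 14 - 1 = 13 days |
| IV antibiotics | 14 | 14 - 7 = 7 days | 14 - 1 = 13 days |
| Investigational therapy | 28 | 28 - 7 = 21 days | 28 - 1 = 27 days |
| Classes with washout None | 0 | 0 | 0 |

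**When there is no shortfall.** The condition is d ≥ W - s. For the 2-week classes, the last intake must be at least 7 days before a Day -7 consent, or at least 13 days before a Day -1 consent. For investigational therapy the corresponding figures are 21 and 27 days.

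**Delaying Day 1 instead.** If Day 1 waits for a washout begun at screening, the screening visit is at least 14 or 28 days old against the 7-day limit in Section 9.5. It is then 14 - 7 = 7 or 28 - 7 = 21 days too old. The serum pregnancy test, where it applies, has its own 7-day limit (Table 1, note 10). Section 9.6.8.1 is not such a limit: it says "All baseline laboratory assessments may occur during screening (within 7 days prior to the first dose of the study drug", which is a permission, and Table 1 schedules safety laboratory tests on Day 1 as well.

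**Widening the window instead.** A window that holds the whole washout would need at least 14 days (participation 14 + 28 = 42 days, 6 weeks) or at least 28 days (28 + 28 = 56 days, 8 weeks).

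**The case against.** The strongest reply is that the existing rules already give the right outcome. A current warfarin user whose Day 1 is at most 7 days away fails exclusion 12. The site can see this at the visit where it records medication, because eligibility is reviewed there. The Day 1 review, the dispensing rule and the no-waiver rule close the remaining gaps. A careful investigator would simply not enrol the subject. Section 9.6.3 also has workable uses: the two classes with no washout, and drugs stopped early enough before consent.

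Most of this stands, and it keeps the point minor. What it does not answer is what happens to the drug. Those rules decide who is dosed. None tells the site to leave warfarin unchanged when the washout cannot fit, and the sentence in Section 9.6.3 is written as a requirement.

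A reader might infer more than the documents support:

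- That subjects could be dosed before their washout ends. The exclusions, the two eligibility reviews, the dispensing rule and the no-waiver rule prevent this.
- That the protocol directs a gap in anticoagulation. It does not: Section 9.6.3 allows replacement, and heparin, enoxaparin and NOACs are permitted.
- That re-screening is forbidden. It is not described, but nothing prohibits it.
- That every IV antibiotic user is excluded by criterion. Exclusion 11 covers only severe infection; the wider rule is the Table 3 washout.

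**Conclusion.** The point holds as a minor matter of subject safety and internal consistency. For a drug still in use at screening, a washout begun after consent is 7 to 13 days short for warfarin and IV antibiotics, and 21 to 27 days short for investigational therapy. The arithmetic is certain, given the stated window and the consent rule in Section 13.2.

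The consequence is less certain. An unnecessary or premature change of warfarin is an inference from the mandatory wording of Section 9.6.3; the documents do not state it as an outcome. Its frequency cannot be sized, because they do not say how many candidates for the 15 places would be taking these drugs. No endpoint, analysis or estimate changes.

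**What to change.** Amend Section 9.6.3 as follows:

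1. Limit the stop-or-replace sentence to the Table 3 classes with washout None (CYP3A and CYP4F2 substrates, herbal and homeopathic remedies).
2. State that a subject whose Table 3 washout for warfarin, IV antibiotics or investigational therapy will not be complete by the planned Day 1 is not dosed in that screening window. The basis is exclusion 12 for warfarin, exclusion 13 for investigational drugs, exclusion 11 for IV antibiotics given for severe infection, and otherwise the Table 3 washout. Exclusion 11 itself should not be widened.
3. State that the site must not stop or switch warfarin in order to meet the current window.
4. State that the subject may be re-screened once the full washout has elapsed after a change made by the treating physician for clinical reasons.

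The cost is a few sentences of protocol text and possibly slightly fewer eligible subjects, partly offset by the explicit re-screening route. This is simpler than lengthening the screening window, which would take participation to 6 or 8 weeks for those subjects.

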# 9.6.4 Physical Examinations and Measurements

A complete physical examination (including a review of the main body organs and systems) must be conducted at screening and the EOS/Early Termination visit (Day 29). In addition, a symptom-driven (abbreviated) physical exam may be performed at the End-of-Treatment (EOT) visit (Day 15), if the investigator deems it clinically indicated; see **Table 1**.

Any treatment-emergent clinically significant physical examination findings should be recorded as adverse events on the Adverse Event CRF.

Subjects will also undergo body weight and height measurement at screening/baseline, and body weight measurements (as part of their standard care on dialysis days) within 60 minutes predialysis and within 60 minutes post-dialysis on each dialysis day during the 2-week treatment period (Visits 1 through 6), at the EOT visit (Day 15), and at the EOS visit (Day 29); see **Table 1**.

#### 9.6.5 Vital Signs Measurements

Vital signs (including blood pressure, heart rate, respiratory rate, and oral body temperature) will be measured at screening, and (as part of their standard care on dialysis days) within 30 minutes pre-dialysis and within 30 minutes post-dialysis at each treatment visit (Visits 1 through 6), at the EOT visit (Day 15), and at the EOS visit (Day 29); see **Table 1**. Any treatment-emergent clinically significant vital signs abnormalities should be recorded as adverse events on the Adverse Event CRF.

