- [6] Standard 12-lead ECG recordings will be obtained within 60 minutes pre-dialysis at screening/baseline, at EOT (Day 15), and at EOS (Day 29). ECG recordings should be performed after the subject has been resting in a supine position for at least 5 minutes, and prior to other procedures scheduled at that same time (e.g., blood draws).

[7] Vital signs (including blood pressure, heart rate, respiratory rate, and oral body temperature) will be measured at screening, and (as part of their standard care on dialysis days) within 30 minutes pre-dialysis and within 30 minutes post-dialysis at each treatment visit (Visits 1 through 6), at EOT (Day 15), and EOS (Day 29).

- [8] All blood sampling will occur pre-dialysis (at the time of needle placement). Hematology panel includes: RBC count, hemoglobin, hematocrit, and WBC count with differential (neutrophils, eosinophils, lymphocytes, monocytes, basophils, and other cells), if clinically indicated. CMP includes: glucose, albumin, total protein, electrolytes (sodium, potassium, bicarbonate, chloride, calcium, magnesium, phosphate), renal function tests (BUN, creatinine), liver function tests (ALT, AST, bilirubin), and lipid profile (total cholesterol, LDL cholesterol, HDL cholesterol, and triglycerides). Coagulation panel includes: PTT, INR, and platelet count.
- [9] Serology for: HIV, HBV (hepatitis B "e" antigen [HBeAg] and PCR for the active virus [HBV DNA]); and HCV (HCV antibody and PCR for active virus [HCV RNA])
- [10] Women of child bearing potential must undergo a serum β-hCG pregnancy test within 7 days prior to the first dose of study drug, and the result must be negative for enrollment.
- [11] All medications (including over-the-counter medications) or therapy administered to the subject during the 30 days prior to the first dose of study drug will be recorded at screening/baseline. Any changes to concomitant medications will be documented regularly throughout the study.

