# 9.5.2 Visit 1 (Day 1, Baseline), Visit 4 (Day 8), Visit 7 (Day 15, End-of-Treatment), and Visit 10 (Day 22) [Mondays]

Subjects will undergo the following assessments during these visits:

- (At baseline/Visit 1 only:) Review of eligibility (inclusion and exclusion) criteria (see Sections 9.1.1 and 9.1.2 for details)
- Recording of any changes in concomitant medications (see Section 9.6.3 for details)
- (At Visit 7 only, if clinically indicated:) Symptom-driven physical examination (see Section 9.6.4 for details)
- (At Visits 1, 4, and 7): Measurement of body weight within 60 minutes pre-dialysis and within 60 minutes post-dialysis (see Section 9.6.4 for details)
- (At Visit 7 only): Standard 12-lead ECG within 60 minutes pre-dialysis (see Section 9.6.6 for details)
- (At Visits 1, 4, and 7): Measurement of vital signs (blood pressure, heart rate, respiratory rate, and oral body temperature within 30 minutes pre-dialysis and within 30 minutes post-dialysis (see Section 9.6.5 for details)
- Collection of blood samples for safety laboratory tests pre-dialysis (hematology, CMP, coagulation panel) (see Section 9.6.8.1 for details)
- (At Visits 1, 7, and 10): Collection of blood samples for biomarker assessments pre-dialysis (pre-dose) (see Section 9.6.8.2 for details):
  - o MGP, osteocalcin, Protein C, PIVKA-II protein, Fetuin A, osteoprotegerin, *hs*-CRP, and Time to Formation of Secondary Calciprotein Particles (T-50 Test); including CPP size.
- Collection of blood samples for PK assessments pre-dialysis/pre-dose (at the time of needle placement) (Visits 1, 4, and 7), during dialysis (Visits 1 and 4) and at the end of dialysis (before needle removal) (Visits 1, 4 and 7) (see Section 9.6.8.3 for details)
- (At Visits 1 and 4 only): Study drug administration pre-dialysis (immediately after needle placement and the pre-dialysis biomarker sampling) (see Section 9.3.5 for details)
- Recording of changes in baseline complaints under general medical history (events occurring before the first dose of study drug [Visit 1 only]; see Section 9.6.2 for details) or AEs (events occurring after the first dose of study drug [Visit 1 post-dose and subsequent visits]; see Section 10.3 for details). Any occurrence of dialyzer clotting (assessed at each dialysis session) is to be recorded as an AE (see Section 10.3.2).

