# 10.3.3.2 Assessment of Causality

The causality assessment for each AE must be completed by the investigator. The investigator should use medical judgment, including knowledge of the subject, the circumstances surrounding the event, and evaluate any potential alternative causes when deciding whether there is a reasonable possibility that the event may have been caused by the investigational product. If there is no valid reason for suggesting a relationship, the AE should be classified as 'not related'. Otherwise, if there is any valid reason, even if undetermined or untested, for suspecting a possible cause-and-effect relationship between the investigational product and the occurrence of the AE, the AE should be assessed as 'related'. The causality assessment must be documented in the source document and the CRF.

Table 5 Guidance for the Assessment of Adverse Event Causality

Term	Relationship	Definition	
Definitively Related	Yes	A clinical event, including laboratory test abnormality that occurs in an apparent time sequence to the administration of the investigational product, is plausible pharmacologically, and cannot be explained by concurrent disease or other drugs or chemicals. Withdrawal of the drug (dechallenge) was followed by improvement or resolution of the event. Recurrence of symptoms on rechallenge (if performed) has occurred.	
Probably Related	Yes	A clinical event, including laboratory test abnormality, with a reasonable time sequence to the administration of the investigational product, unlikely to be attributed to concurrent disease or other drugs or chemicals. Withdrawal of the drug (dechallenge) was followed by improvement or resolution of the event. Rechallenge information is not required to fulfil this definition.	

Term	Relationship	Definition	
Possibly Related	Yes	A clinical event, including laboratory test abnormality, for which a time relationship with the administration of the investigational product may exist, but which could also be explained by concurrent disease or other drugs or chemicals. Information on drug withdrawal may be lacking or unclear.	
Unlikely Related	No	A clinical event, including laboratory test abnormality, with a doubtful temporal relationship to the administration of the investigational product, and in which other concomitant drugs, chemicals or the subject's underlying disease provide plausible explanations for the event.	

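### Vital signs are scheduled at 7 of 7 dialysis sessions to Day 15 but at 1 of 6 afterwards, so change during most of the washout is unobserved and vital-sign AE detection is less complete after Day 15

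*Combined protocol and SAP*

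**What the plan says.** The schedule is stated consistently throughout the protocol. Section 9.6.5 places the pre- and post-dialysis readings "at each treatment visit (Visits 1 through 6), at the EOT visit (Day 15), and at the EOS visit (Day 29", and note [7] to Table 1 repeats this: "pre-dialysis and within 30 minutes post-dialysis at each treatment visit (Visits 1 through 6), at EOT (Day 15), and EOS (Day 29". The visit lists agree. For Mondays, Section 9.5.2 has "At Visits 1, 4, and 7): Measurement of vital signs", which leaves out Visit 10 (Day 22). For Wednesdays and Fridays, Section 9.5.3 has "At Visits 2, 3, 5, and 6): Measurement of vital signs", which leaves out Visits 8, 9, 11 and 12 (Days 17, 19, 24 and 26). Section 9.5.4 brings the readings back on Day 29.

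Four other provisions bear on this:

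- Section 9.5: "At each study visit, subjects will also undergo hemodialysis, as per their standard ESRD management". Section 9.6.5 describes the vital signs as part of routine dialysis-day care.
- Section 9.6.5: "Any treatment-emergent clinically significant vital signs abnormalities should be recorded as adverse events".
- Section 11.6 lists change from baseline in vital signs as a secondary safety endpoint. It defines one treatment-emergent window, from first dose to last study visit. Its subsections cover AEs, concomitant medications, laboratory parameters and ECG; none covers vital signs.
- Section 11.11: data are summarised as observed, without imputation.

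**The concern.** The last two weeks of the study are meant as safety follow-up, and this is the first use of EPN-701 in humans. With no control arm, what happens to blood pressure and heart rate as drug leaves the body is one of the few internal signals available. The schedule provides no reading in that interval. Pharmacokinetic blood is drawn on Day 17 and safety laboratory blood on Day 22, but no vital signs accompany either. A change that appears, persists or reverses between Day 15 and Day 29 would not show in the endpoint summaries.

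The second issue is ascertainment. A clinically significant vital-sign abnormality becomes an AE and so enters the primary endpoint. Within one treatment-emergent window, this source of AEs is looked for at every session early on and at one session in six later. A reader who compares the two periods would partly be comparing how often someone was asked to record a reading.

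**Working it through.** **Visit count.** Section 9.5 says: "Subjects will undergo a total of 14 visits during their study participation". Screening plus Days 1, 3, 5, 8, 10, 12, 15, 17, 19, 22, 24, 26 and 29 gives 1 + 13 = 14, so the stated figure is reproduced.

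**Coverage, Day 1 onwards.** Vital signs are scheduled on Days 1, 3, 5, 8, 10, 12, 15 and 29.

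| Split | Earlier period | Later period |
|---|---|---|
| At Day 15 | 7 of 7 sessions (14 readings) | 1 of 6 (2 readings) |
| At last dose, Day 14 | 6 of 6 on drug | 2 of 7 off drug |

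The second row follows Table 1 and Section 9.3.5, which dose for 14 days. The Day 15 pharmacokinetic text (synopsis, Table 1 note [14], Section 9.6.8.3) has study drug given after that day's sample. These passages conflict and must be reconciled. The imbalance is present under either split.

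**Drug remaining during the gap.** The half-life is given as 72 h in Section 6.1.2 and 68 h in Section 6.2.3, both for MK-7 from published work. Residual = 2^(-h/t), with h the hours since a Day 14 dose and t the half-life.

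| Day | h | t = 68 | t = 72 |
|---|---|---|---|
| 15 | 24 | 78% | 79% |
| 17 | 72 | 48% | 50% |
| 22 | 192 | 14% | 16% |
| 26 | 288 | 5% | 6% |
| 29 | 360 | 3% | 3% |

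Readings exist at the top and bottom of this table and nowhere between. If a dose were also taken on Day 15, h falls by 24: Day 17 becomes 61-63% and Day 22 becomes 18-20%, and the picture is the same.

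**AE detection.** Let c be the share of clinically significant abnormalities at the five unscheduled sessions that are still captured through routine care and AE recording. The documents do not give c, so the full range is shown. Assume the same risk at every session and full capture where readings are scheduled. Detection per session after Day 15, relative to before, is (1 + 5c)/6.

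- c = 0: 1/6 = 0.17
- c = 0.5: 3.5/6 = 0.58
- c = 1: 6/6 = 1.00

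Split at the Day 14 dose, the ratio is (2 + 5c)/7: 0.29, 0.64 and 1.00.

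**Mean change from baseline.** With no drug effect, the expected change at any visit is 0, whatever the number of visits. With an assumed within-subject SD of 10 and n = 15, its standard error is √(2 × 10²/15) = 3.65 at each visit, including Day 29. Fewer visits leave a gap; they do not shift the mean.

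**Cost of closing the gap.** 5 sessions × 2 readings = 10 per subject; 10 × 15 = 150.

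**The case against.** The strongest reply is that the follow-up visits are not blind to vital signs. AEs and medication changes are recorded at Visits 8-12, staff dialyse the subject at each one, and Section 12.3.1 lists dialysis flowsheets among the source documents. Section 10.1 defines a clinically significant abnormality through symptoms, a change in study treatment, an intervention or investigator judgment, and most of these should surface without an eCRF field. This stands, and it is why c could be well above zero. It does not make c equal to 1, because capture then relies on someone noticing a reading the protocol does not ask them to record. It also does nothing for the change-from-baseline endpoint.

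Four stronger readings are tempting, and the documents do not support them.

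- A reader might infer that vital-sign change and AEs must fall when drug stops. Mean change by visit does not fall, and the fall in AE detection is of unknown size.
- A reader might infer a seven-fold drop in AEs from 7 sessions against 1. That sets capture at Visits 8-12 to zero, compares periods with different numbers of sessions, and counts Day 15 as on drug. Section 11 plans no comparison of on-drug with off-drug periods.
- A reader might take Day 29 as the only off-drug reading. With a Day 14 last dose, Day 15 is also off drug, though with most of the drug still present.
- Table 5 counts towards a related classification that "Withdrawal of the drug (dechallenge) was followed by improvement or resolution of the event", so a reader might infer that causality is judged on missing data. Section 10.3.4 has known AEs followed until resolved or stable, with tests when appropriate. The gap bears on finding new events more than on following known ones.

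**Conclusion.** The point holds as a gap in observation and an imbalance in ascertainment. The counts are exact: 7 of 7 sessions against 1 of 6, or 6 of 6 against 2 of 7 by dosing. Vital-sign change has no scheduled reading while residual drug falls from about 78-79% to about 3%. That range assumes simple exponential decline at the published MK-7 half-lives, which may not hold for EPN-701 in hemodialysis patients. Detection of vital-sign AEs after Day 15 lies between 0.17 and 1.00 of the earlier per-session level; the plan gives nothing to narrow that range.

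This does not bias the planned visit-wise means, and it does not undermine the primary endpoint taken as one window. It limits what can be said about vital signs after Day 15, and it makes raw vital-sign AE counts from the two periods non-comparable. It is worth correcting mainly because the correction is so cheap.

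**What to change.** In Table 1 and its note [7], Section 9.5.2 (Visit 10), Section 9.5.3 (Visits 8, 9, 11 and 12) and Section 9.6.5, have the routine pre- and post-dialysis vital signs at Visits 8-12 entered on the eCRF. All 13 sessions from Day 1 to Day 29 are then covered alike. In Section 11.6, add a vital-signs summary that gives change from baseline at each of these visits.

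The cost is transcribing about 10 readings per subject, about 150 in all, with no added visit or procedure. This presumes that the routine readings continue after Day 15, which Sections 9.5 and 9.6.5 together imply.

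If the schedule is kept, report vital-sign AEs per recorded session and state that raw counts before and after Day 15 should not be compared. Do not restrict the AE summaries to Days 1-15: that would discard treatment-emergent events, including any found on Day 29.
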